10.1.4 Safety Endpoint

A safety endpoint will be the percentage of subjects with treatment-emergent AEs (TEAEs), with treatment-emergent defined as occurring upon or after administration of the first dose of study drug.

10.2 Hypotheses

The primary efficacy endpoint of the study is percentage of subjects at the Test of Cure Visit with “therapeutic cure”, defined as “mycological cure” plus “clinical cure” for the study ear. Mycological cure is defined as a negative mycological culture, and clinical cure is defined as the absence of all otomycosis signs and symptoms based on investigator assessment according to the scales for each individual sign or symptom.

Analysis is based on the following hypothesis:

$$H_0: p_T - p_V = 0$$

$$H_1: p_T - p_V > 0.$$

where H_0 is the null hypothesis, H_1 the alternative hypotheses, and p_T and p_V are percentage of subjects with success in the Treatment (miconazole oil) and Vehicle (vehicle oil) groups, respectively. Comparisons between groups for the difference in the percentage of subjects achieving the primary endpoint of therapeutic cure will be conducted using a chi-square test with a 2-sided significance level of 0.05.

Comparisons will also be conducted similarly between the miconazole oil and vehicle oil groups for the secondary endpoints of clinical cure, and mycological cure.

10.3 Sample Size

For the Randomization Period, approximately 128 subjects (~64 in each group) are required to provide 80% power, using a chi-square test with a 2-sided significance level of 0.05, assuming a response rate for the primary efficacy endpoint of 25.0% in the miconazole oil group and 7.1% in the vehicle oil group.

The sample size of 220 subjects for Enrollment A assumes that ~58% of subjects enrolled into Enrollment A will have a positive fungal culture at Screening/Baseline and will therefore be included in the MITT population. This number may be higher or lower depending on the percentage of subjects eligible to be included in the MITT population.

The estimated sample size of 170 subjects for Enrollment B is not based on statistical considerations and is instead based on the achievement of at least 300 subjects who have been exposed to miconazole oil for 14 days who are evaluable for safety (see also Section 3.4.2).

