The mechanisms of action of miconazole when used topically for the treatment of fungal infections involve its actions against the fungal organisms, rather than their human host. Miconazole targets the cytochrome P450-dependent enzyme 14- α -sterol demethylase, an enzyme that is also involved in mammalian cholesterol synthesis, resulting in inhibition of ergosterol biosynthesis in the cell membrane. Because ergosterol is an important component of the cell membrane, inhibition of its synthesis inhibits fungal cell growth [Vandenbosch 2012]. In addition to its activity toward the enzyme 14- α -sterol demethylase, miconazole also leads to increased reactive oxygen species in fungal organisms, which appears to result in fungicidal activity [Vandenbosch 2010; Musaji 2010].

The mechanisms of action of miconazole against fungi in general appear to be applicable to fungi associated with otomycosis. Data from a recently-completed Phase 2 study of the investigational product (2% miconazole oil; Hill Dermaceuticals, Inc. Study HD-MCZ-PHII-DRF062016) demonstrated 25.0% of subjects with therapeutic cure, defined as a negative fungal culture plus the absence of each of the otomycosis signs and symptoms of pruritus, debris, fungal elements, and pain, compared with 7.1% of subjects treated with control product (vehicle oil), at the final test of cure study visit, following a 14-day treatment regimen. The percentage of subjects with therapeutic cure following a 7-day treatment regimen was 8.3%, supporting the 14-day treatment duration for miconazole.

Clinical studies of 2% miconazole conducted outside of the United States also suggest the efficacy of miconazole in the treatment of human otomycosis [Kiakojuri 2007; Vennewald 2010; Navaneethan 2015]. *In vitro* studies of miconazole have also demonstrated activity of miconazole against some clinical isolates of fungi associated with human otomycosis in the US [Bassiouny 1986; Stern 1988].

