Adverse event (AE) data from the recently-completed Phase 2 study of the investigational study support the acceptable safety of miconazole oil and generally demonstrated a lower percentage of patients with treatment-emergent AEs (TEAEs) in each of the miconazole oil groups (which were treated for either 7 or 14 days) compared with the vehicle oil group (which was treated for 14 days). The most frequently reported TEAEs in the 14-day miconazole oil group in the Phase 2 study were application site pruritus, application site pain, and ear infection fungal (Table 1). In each case except for ear infection fungal, a higher percentage of subjects in the 14-day vehicle oil group compared with the 14-day miconazole oil group reported the TEAE. Similar results were observed for the 7-day miconazole oil group, although a higher percentage of subjects in the 7-day miconazole oil group had the TEAE of application site infection compared with the 14-day miconazole oil and 14-day vehicle oil groups.

Table 1 Treatment-emergent Adverse Event Preferred Terms Reported in >1 Patient in the Safety Population of Hill Dermaceuticals, Inc. Study HD-MCZ-PHII-DRF062016

System Organ Class Preferred Term	Study Group		
	7-Day Miconazole Oil (N=23) n (%)	14-Day Miconazole Oil (N=22) n (%)	14-Day Vehicle Oil (N=20) n (%)
Ear and labyrinth disorders	0 (0.0)	0 (0.0)	4 (20.0)
Ear pain	0 (0.0)	0 (0.0)	2 (10.0)
Tympanic membrane perforation	0 (0.0)	0 (0.0)	2 (10.0)
General disorders and administration site conditions	4 (17.4)	6 (27.3)	9 (45.0)
Application site pain	1 (4.3)	2 (9.1)	5 (25.0)
Application site pruritus	3 (13.0)	4 (18.2)	6 (30.0)
Infections and infestations	4 (17.4)	3 (13.6)	2 (10.0)
Application site infection	2 (8.7)	0 (0.0)	0 (0.0)
Ear infection fungal	1 (4.3)	2 (9.1)	1 (5.0)

Source: Study HD-MCZ-PHII-DRF062016 Clinical Study Report Table 18

No serious AEs (SAEs) were reported in the Phase 2 study. AEs leading to discontinuation in the Phase 2 study were observed in a higher percentage of subjects in the 14-day vehicle oil group compared with either the 14-day miconazole oil or 7-day miconazole oil group, providing further evidence of an acceptable safety profile for miconazole oil (Table 2).

Table 2 Treatment-emergent Adverse Event Leading to Permanent Withdrawal of Study Drug and/or Early Discontinuation from the Study in the Safety Population of Hill Dermaceuticals, Inc. Study HD-MCZ-PHII-DRF062016

Preferred Term	Study Group		

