3.4.2 Enrollment B

An estimated 170 eligible subjects are planned to be enrolled in order to achieve at least 300 total subjects in the study (including both Enrollment A and Enrollment B) who are exposed to miconazole oil for 14 days who are evaluable for safety. This number has been estimated on the basis of the following assumptions:

- A total of 220 subjects will be enrolled into the Randomization Period of Enrollment A, with 110 subjects exposed to active treatment with miconazole oil (on the basis of the 1:1 randomization for the Randomization Period), and 110 subjects exposed to the vehicle treatment:

- Of the 110 subjects exposed to active treatment (miconazole oil) in the Randomization Period, ~90% (100 subjects) will complete the full 14 days of treatment, with the remaining ~10% (10 subjects) completing less than the 14-day treatment course
- Of the 110 subjects exposed to vehicle treatment in the Randomization Period, ~50% (55 subjects) will opt to participate in the Optional Open-label Extension of Enrollment A, with the other ~50% (55 subjects) concluding participation in the study
- Of the 55 subjects exposed to miconazole oil treatment in the Optional Open-label Extension, ~90% (50 subjects) will complete the full 14 days of treatment, with the remaining ~10% (5 subjects) completing less than the 14-day treatment course
- On the basis of these assumptions, ~150 subjects will have been exposed to miconazole oil for the full 14-day treatment during Enrollment A (100 subjects during the Randomization Period and 50 subjects during the Optional Open-label Extension), and an additional ~150 subjects exposed to miconazole oil for the full 14-day treatment will be needed to achieve the ≥ 300 total subjects required to be exposed to miconazole oil for the full 14-day treatment
- Assuming ~90% of subjects enrolled into Enrollment B complete the full 14 days of open-label treatment with miconazole oil, ~170 subjects will be required to be enrolled in Enrollment B in order to achieve ~150 subjects who complete the full 14-day treatment with miconazole oil
- Therefore, ~150 subjects from Enrollment A and ~150 subjects from Enrollment B are estimated to be needed for at least 300 total subjects in the study who are exposed to miconazole oil for a full 14 days.

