The actual number of subjects enrolled into Enrollment B may therefore be higher or lower than 170 depending on the accuracy of the assumptions as stated above, including the number of subjects who have completed a full 14 days of treatment with miconazole oil in Enrollment A as well as in Enrollment B. Enrollment will continue into Enrollment B until the required number of subjects exposed to miconazole oil for 14 days and evaluable for safety has been achieved.

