7.4 Otomycosis Signs and Symptoms

The signs and symptoms of otomycosis will be assessed according to the scales for pruritus (see Section 7.4.1), debris (see Section 7.4.2), presence of fungal elements (see Section 7.4.3), and aural fullness (see Section 7.4.4). The same evaluator should assess each subject for signs and symptoms of otomycosis at each visit throughout the subject's participation in the study, if possible.

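### Is 128 MITT subjects too few, given that the planned cure rates are undiscounted Phase 2 estimates on a slightly different composite?

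*Combined protocol and SAP*

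**What the plan says.** Section 10.3 (repeated in the Synopsis) calls for about 128 subjects, 64 per arm, for 80% power with a chi-square test at two-sided 0.05, "assuming a response rate for the primary efficacy endpoint of 25.0% in the miconazole oil group and 7.1% in the vehicle oil group". About 58% of those enrolled are expected to be culture-positive, which gives 220 for Enrollment A. Sections 3.4.1 and 4.3 treat 128 as a minimum.

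Section 1.1 gives the source of the rates. The Phase 2 study defined therapeutic cure as a negative culture plus "absence of each of the otomycosis signs and symptoms of pruritus, debris, fungal elements, and pain, compared with 7.1% of subjects" on vehicle, and found 25.0% on 14-day miconazole oil. For the 7-day arm, "The percentage of subjects with therapeutic cure following a 7-day treatment regimen was 8.3" per cent. Table 1 lists Phase 2 safety arms of 23, 22 and 20. No cure counts or efficacy denominators are given. Section 7.4 of the present protocol scores pruritus, debris, fungal elements and aural fullness; pain is not scored.

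The Enrollment B figure of 170 "is not based on statistical considerations and is instead based on the achievement of at least 300 subjects" with a full 14-day exposure. Section 3.4.2 says the number enrolled "may therefore be higher or lower than 170 depending on the accuracy of the assumptions as stated above".

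**The concern.** Efficacy rests on one comparison, and Section 10.5.1.1 gates both secondary tests behind it. The effect size is the Phase 2 point estimate, used without a discount. It seems to come from about four cures, on a composite with a different symptom in it. Section 10.3 does not discuss either point. It also does not say whether the assumed rates already count missing outcomes as failures, as Section 10.5.4 requires. Enrollment A closes on a count of MITT subjects, and the plan does not check the assumed rates along the way.

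Meanwhile about 170 subjects are planned for Enrollment B, which adds no efficacy information. Moving part of that effort into the randomized comparison looks like a cheap way to buy power. If the true effect is smaller than 17.9 points, the trial could fail although a useful effect exists.

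**Working it through.** **Inputs.** From Section 10.3: rates 0.25 and 0.071, two-sided 0.05, 64 per arm, 58% culture-positive. From Section 3.4.2: 90% complete 14 days, 50% of vehicle subjects enter the extension, and 90% of those complete it. Safety arm sizes come from Table 1.

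**1. The plan's own figure.** Pooled-variance formula, with mean rate (0.25 + 0.071)/2 = 0.1605:

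n = [1.960·√(2 × 0.1605 × 0.8395) + 0.8416·√(0.25 × 0.75 + 0.071 × 0.929)]² / 0.179²
= (1.0174 + 0.4237)² / 0.03204 = 64.8, so 65 per arm.

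Power at 64 per arm: Φ[(0.179 × 8 − 1.0174)/0.5034] = Φ(0.823) = 79.5%. The exact power of the chi-square test is 81.0%. The stated 128 is reproduced to within 2 subjects.

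**2. What the Phase 2 percentages can be.** This assumes that efficacy denominators did not exceed the safety arm sizes. Then 7.1% (n ≤ 20) can only be 1/14, and 8.3% (n ≤ 23) only 1/12. The 25.0% (n ≤ 22) can be 1/4, 2/8, 3/12, 4/16 or 5/20. With 3/12 the denominators total 12 + 14 + 12 = 38 of 65, or 58.5%, close to the 58% in Section 10.3. That supports 3/12 but remains an inference. Exact 95% intervals are 5.5-57.2% for 3/12 and 0.2-33.9% for 1/14; Fisher p = 0.31.

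**3. Sensitivity in both directions.** Same formula:

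| Active vs vehicle | 64 per arm | 87 per arm |
|---|---|---|
| 25% vs 7.1% (plan) | 79.5% | 90.2% |
| 22% vs 7.1% | 67% | 80% |
| 25% vs 10% | 61% | 74% |
| 20% vs 7.1% | 57% | 70% |
| one more vehicle cure: 25% vs 2/14 | 33% | 43% |
| one fewer active cure: 2/12 to 4/20 vs 1/14 | 38-57% | 49-70% |
| one more active cure: 6/20 to 4/12 vs 1/14 | 92-97% | 98-99% |

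With no vehicle cures, power at 64 per arm would be about 99%. The one-cure ranges cover active denominators of 12 to 20.

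**4. Power averaged over the Phase 2 uncertainty.** Beta posteriors with uniform or Jeffreys priors, for 3/12, 4/16 or 5/20 against 1/14, give 55-61% at 64 per arm and 61-67% at 87 per arm. These priors pull the mean vehicle rate up from 7.1% to (1+1)/(14+2) = 12.5% or (1+0.5)/(14+1) = 10%, so the averages lean pessimistic on the vehicle side.

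**5. What 90% would cost.** Replacing 0.8416 by 1.2816 gives (1.0174 + 0.6452)²/0.03204 = 86.3, so 87 per arm or 174 MITT. Enrollment A becomes 174/0.58 = 300 (+80, about 40 on vehicle). Full exposures per Enrollment A subject are 0.5 × 0.9 + 0.5 × 0.5 × 0.9 = 0.675, so 300 subjects give 202.5. Enrollment B then needs (300 − 202.5)/0.9 = 108.3, so 109 instead of 170. The total is 409 against 390, a net increase of 19. Before rounding the increase is 20, ranging from +12 to +32 if extension uptake is 70% down to 20%.

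**6. Missing outcomes.** If the assumed rates do not already count missing as failure, and if 10% were missing in each arm (an assumption), the rates become 22.5% and 6.39%, with power 74% at 64 per arm and 86% at 87.

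**The case for a change.** The best argument for a change is that it is unusually cheap. Three quarters of the extra Enrollment A subjects are offset in Enrollment B, because 0.675/0.9 = 0.75. The exposure target is still met on the plan's own assumptions, and Section 3.3 already prefers Enrollment A for anyone eligible for both parts. At a 7.1% vehicle rate, the active rate detectable with 80% power would fall from about 25% to about 22%. The evidence behind the planned effect is thin on any reading: even 5/20 against 1/14 has Fisher p = 0.36.

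All of this stands as fact, but it does not show a fault. The larger size adds only about 6 points of averaged power, and with a vehicle rate of 2/14 it would still have only 43%. The net +20 also understates the burden. Enrollment A grows by 80/220 = 36%, and Section 3.3 expects recruitment to that part to slow in winter. Nor would a somewhat smaller effect probably be missed: 57-61% power at differences of 12.9 and 15.0 points means detection is more likely than not. Power drops below 50% only further out (25% vs 12%: 47%; 18% vs 7.1%: 46%).

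The change from pain to aural fullness has no known direction, so it does not argue for a larger number. Naming the Phase 2 counts and adding a sensitivity table would inform readers but alter no result. With vehicle at 7.1%, the difference that 128 subjects can detect with 80% power is already the one in Section 10.3.

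**Conclusion.** No change is needed. The sample size calculation is correct and the stated 80% power is delivered (79.5% by formula, 81.0% exactly). The assumptions are optimistic in the ordinary sense that Phase 2 estimates are carried forward undiscounted, and power is sensitive to them in both directions. Going to 174 MITT subjects would be a fair choice but not a correction. It reaches 90% only if 25.0% and 7.1% are true, gives 74% or 70% under the two modest departures, and adds 80 randomized subjects to a condition that is seasonally hard to recruit. Whether that is worth about 20 more subjects overall is a trade-off for the sponsor.

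The conclusion does not depend on the inferred Phase 2 counts, since the stated power is reproduced from Section 10.3 alone. The averaged-power figures do depend on those counts and on the priors. The net enrolment figure depends on the completion and extension uptake rates in Section 3.4.2.

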10.4 Study Populations

10.4.1 Intent-to-treat Population

The intent-to-treat (ITT) population will be defined as all subjects who were randomized.

10.4.2 Modified Intent-to-treat Population

The modified intent-to-treat (MITT) population will be a subset of the ITT population. The MITT population will include subjects in the ITT population with a positive fungal culture at Screening/Baseline. The MITT population will be the primary population to assess efficacy.

10.4.3 Per Protocol Population

The per protocol (PP) population will be a subset of the MITT population and will include all subjects who complete the Test of Cure visit without any major protocol violations. The PP population will include subjects in the MITT population who did not meet any of the following criteria:

- Violated the inclusion/exclusion criteria
- Used an interfering concomitant medication
- Did not attend the Test of Cure visit
- Did not attend the End of Treatment visit
- Have not been compliant with the dosing regimen (i.e., subjects must have received 80%-120% of the expected applications of study medication in the study ear during participation in the study)
- Out of visit window at the Test of Cure Visit (-1/+8 days)

Subjects who discontinue from the study due to an adverse event related to study treatment, documented lack of treatment effect, or worsening of condition will be included in the PP population. Prior to breaking the blind, other additional criteria may be added to the list to accommodate for unforeseen events that occurred during the conduct of the trial that result in noteworthy study protocol violations.

All efficacy analyses will be performed using the PP population in a supportive manner.

10.4.4 Safety Population

Two safety populations will be defined.

The Randomization Period safety population will include all subjects who received at least one dose of study drug and had at least one post-Baseline safety assessment during the Randomization Period.

The Open Label safety population will include all subjects who received at least one dose of miconazole oil and had at least one post-Baseline safety assessment during the Optional Open-label Extension or Enrollment B.

Safety analyses for the Randomization Period will be performed using the Randomization Period safety population. Safety analyses for the Optional Open-label Extension and Enrollment B will be combined and presented using the Open Label safety population.

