3 STUDY DESIGN

This study will be conducted in 2 portions (see also Figure 1 for a schematic diagram of the study design):

1. Enrollment A, which will consist of 2 treatment periods as follows and will be conducted in subjects with otomycosis:
 - a. A randomized, double-blind, parallel-group treatment period. This treatment period will be referred to as the "Randomization Period" and will be followed by:
 - b. An optional, open-label treatment period with miconazole oil. This treatment period will be referred to as the "Optional Open-label Extension."
2. Enrollment B, which will consist of open-label treatment with miconazole oil in subjects who will not be required to have signs and symptoms of otomycosis.

Figure 1: Diagram of Study Design

- Subjects must meet all eligibility criteria in Section 4.1 to be randomized in Enrollment A.
- Subject must have a visual presence of fungal elements to be enrolled in the Optional Open-label Extension.
- Subject must meet all eligibility criteria in Section 4.2 to receive treatment with miconazole oil in Enrollment B.

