3.2 Enrollment B

Enrollment B may be initiated while Enrollment A is still actively enrolling subjects. An estimated 170 male or female subjects will receive study drug (miconazole oil) in Enrollment B, although this number may be higher or lower depending on the total number of subjects needed to achieve at least 300 subjects who are exposed to miconazole oil for 14 days in the study overall who are evaluable for safety.

At Screening/Baseline (Day B1), potentially eligible subjects will provide informed consent, and subjects will undergo screening evaluations to include a physical examination and an evaluation of medical history. Urine will be obtained for pregnancy screening in female subjects of childbearing potential. Prior and concomitant medications will be reported. Subjects who meet all eligibility criteria will be entered into the study. Study drug will be weighed and dispensed to the subject along with a subject diary. The subject will then begin treatment with miconazole oil. In subjects who do not have otomycosis, treatment will be in the left ear if both ears are otherwise eligible; if only one ear is eligible, treatment will be in that ear. In subjects who have otomycosis (i.e., any signs and/or symptoms consistent with a clinical diagnosis of otomycosis in the judgment of the investigator), treatment will preferably be in the ear(s) with otomycosis, provided the ear(s) meet all eligibility criteria. If both ears are judged by the investigator to have otomycosis and both meet all eligibility criteria, both ears may be treated. The subject or caregiver will instill the first dose of miconazole oil at the site, under the supervision of the investigator or site personnel. AEs will then be assessed. The subject will then leave the clinic and continue to administer miconazole oil and to complete the subject diary twice per day, following the same instructions for miconazole oil administration as in Enrollment A.

Subjects will return to the clinic on Day B15 for the End of Treatment Visit, at which time AEs and concomitant medications will be assessed. Subjects will return all unused miconazole oil along with the completed subject diary. A urine pregnancy test will be performed in women of childbearing potential.

Safety assessments will include AEs.

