4.2 Enrollment B

4.2.1 Inclusion Criteria

In order to be eligible for Enrollment B, subjects must meet all of the following criteria:

1. Male or non-pregnant, non-lactating females
2. Presence or absence of uncomplicated otomycosis of the external ear only, with otomycosis defined as the presence of any signs and/or symptoms consistent with a clinical diagnosis of otomycosis in the judgment of the investigator
3. General good health as determined by medical examination and medical history, and who are free of clinically significant disease, including diabetes mellitus that is not well-controlled or that could interfere with the study
4. Females of childbearing potential must have had a negative urine pregnancy test at Screening/Baseline and must agree to use an effective method of contraception (as defined in Section 8.5) from Screening/Baseline up through the final study visit. Females of childbearing potential include any female who has experienced menarche and who has not undergone successful surgical sterilization (hysterectomy, bilateral tubal ligation or bilateral oophorectomy) or is not postmenopausal (defined as amenorrhea >12 consecutive months). Females who are using oral, implanted, or injectable contraceptive hormones, an intrauterine device (IUD), barrier methods (diaphragm, condoms, spermicide) to prevent pregnancy,

practicing abstinence or where partner is sterile (e.g., vasectomy), should be considered to be of childbearing potential

5. Subjects and/or their caregivers (as appropriate for the age of the subject) must have full legal capacity to volunteer
6. Subjects and/or their caregivers must have completed an appropriately administered institutional review board (IRB)-approved informed consent and assent (as applicable) prior to any study related procedures
7. Subjects and their caregivers (as applicable) must agree to comply with all requirements of the protocol
8. For subjects with only one ear meeting all study eligibility criteria, the subject will be eligible for the study, and the ear meeting all eligibility criteria will be treated with study drug. In subjects who do not have otomycosis, treatment will be in the left ear if both ears are otherwise eligible. In subjects who have otomycosis, treatment will be in the ear(s) with otomycosis, provided the ear(s) meets all eligibility criteria. If both ears are judged by the investigator to have otomycosis and both meet all eligibility criteria, both ears may be treated.

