8 ADVERSE EVENTS

8.1 Definition of an Adverse Event

An AE is any untoward medical occurrence in a subject or clinical investigation subject administered a study drug and which does not necessarily have a causal relationship with the study drug. An AE can therefore be any unfavorable and unintended sign (including a clinically significant abnormal laboratory finding), symptom, or disease temporally associated with the use of an investigational or marketed study drug, whether or not considered related to the investigational or marketed study drug. AEs include any illness, sign, or symptom that has appeared or worsened during the course of the clinical trial, regardless of causal relationship to the study drug. Study drug includes the investigational drug under evaluation and the comparator product.

Medical conditions/diseases present before signing the informed consent form are only considered AEs if they worsen after the informed consent form is signed.

AEs may be either spontaneously reported or elicited during questioning and examination of a subject. At each examination or visit, study personnel will ask each subject the following question, "Have you had any problems since we last spoke?" If known, the investigator should report the diagnosis of the underlying illness or disorder, rather than its individual symptoms.

The worsening or reoccurrence as compared to any previous visit in a subject of any symptom of otomycosis (including any increase in numerical score for pruritus and/or aural fullness according to the scales presented in Section 7.4, and/or any other symptom of otomycosis that worsens but is not captured in the scales presented in Section 7.4) should be reported as an AE. The diagnosis of the underlying disease or disorder should be reported as the AE, if known. For example, if the worsening symptom is believed to be due to otomycosis, the AE should be reported as “worsening of disease under study.” If the worsening symptom is believed to be due to some other cause (such as bacterial infection), that underlying illness or disorder should be reported as the AE.

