10.5.2 Safety Analyses

Safety summaries will be conducted using two safety populations (see Section 10.4.4). All AEs occurring during the study will be recorded and classified using terminology from the Medical Dictionary for Regulatory Activities (MedDRA). All reported treatment-emergent adverse events (TEAEs), defined as any AE with an onset on or after the date of first study drug application, will be summarized. Summaries will provide the number of subjects reporting TEAEs, system organ class, preferred term, severity, and relationship to study drug. When summarizing TEAEs by severity or relationship to study drug, each subject will be counted only once within a system organ class or a preferred term using the event with the greatest severity or causality, respectively, within each category. All reported SAEs will be summarized by the number of subjects reporting the event, system organ class, preferred term, severity, and relationship to study drug.

Summaries will be provided separately for the blinded and unblinded portions. Specifically, summaries will be provided by treatment group for the Randomization Period using the Randomization Period safety population, and for all open-label subjects using the Open Label safety population.

All information pertaining to AEs noted during the study will be listed by study portion (Enrollment A or Enrollment B), study period (Randomization or Optional Open-label), as applicable, treatment group, and subject and will include a verbatim description of the event as reported by the investigator, as well as the preferred term, system organ class, start date, stop date (if stopped), seriousness, severity, action taken regarding the study drug, corrective treatment, outcome, and relationship to the study drug. In addition, a listing of subjects who prematurely discontinue from the study due to AEs will be provided as well as a listing of subjects who report an SAE.

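### Open-label adverse-event summaries combine the extension with Enrollment B, so the pooled rate describes neither group; show them separately beside the total

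*Combined protocol and SAP*

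**What the plan says.** Section 10.4.4 defines a single Open Label safety population and states that "Safety analyses for the Optional Open-label Extension and Enrollment B will be combined and presented using the Open Label safety population". Section 10.5.2 repeats the rule: open-label summaries are given "and for all open-label subjects using the Open Label safety population". The AE listings are treated differently. They "will be listed by study portion (Enrollment A or Enrollment B), study period (Randomization or Optional Open-label"), among other keys. Section 10.5.6 plans subgroup summaries for the primary and secondary endpoints only, so no safety summary by portion or disease status is planned there.

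The two groups are defined differently. Section 3 describes Enrollment B as "open-label treatment with miconazole oil in subjects who will not be required to have signs and symptoms of otomycosis", and inclusion criterion 2 in section 4.2.1 admits "Presence or absence of uncomplicated otomycosis of the external ear only". Under section 3.1.2, an extension subject must have visible fungal elements in an ear treated during the Randomization Period.

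The assessments also differ. Section 3.2 says of Enrollment B: "Subjects will return to the clinic on Day B15 for the End of Treatment Visit, at which time AEs and concomitant medications will be assessed". Table 4 has no row for otomycosis signs and symptoms; section 7.2 adds an ear examination, without scores. Extension subjects are scored at Day OLE15 (Table 3, section 6.1.3.2). Section 8.1 makes worsening of an otomycosis symptom reportable as an AE, "including any increase in numerical score for pruritus and/or aural fullness".

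For the blinded part, section 10.5.2 says "summaries will be provided by treatment group for the Randomization Period using the Randomization Period safety population".

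**The concern.** A TEAE percentage is interpretable when its denominator is one recognizable population and its events were found in one way. The open-label table has neither property. It joins subjects with fungal elements still visible after a randomized course to subjects who may have healthy ears. One kind of event, a rise in a symptom score, can be detected by scale in the first group but not in the second.

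The groups differ in other respects too. The extension takes subjects from either randomized arm, so it mixes first and second miconazole courses. Concomitant-medication limits are wider in Enrollment A (section 5.1.2) than in Enrollment B (section 5.2.2). Enrollment B subjects without otomycosis are treated in one ear, whereas extension subjects may be treated in both.

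At stake is what the open-label tables can show. If rates differ between the groups, the pooled figure hides it, and its value depends on how many Enrollment B subjects happened to be enrolled. Section 3.4.2 allows that number to move up or down to reach the exposure target.

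**Working it through.** **Inputs, all from section 3.4.2 unless stated.** 110 subjects per randomized arm; about 50% of vehicle subjects enter the extension; about 90% complete 14 days in each part; 170 in Enrollment B. The protocol gives no number of active-arm subjects entering the extension, although section 3.1.2 admits them. I take 0 to 55 as an assumed range, the upper end matching the vehicle figure.

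**1. Reproduce the plan's own figure.**
- Active arm completing: 110 × 0.9 = 99 (protocol 100).
- Vehicle subjects entering the extension: 110 × 0.5 = 55; completing: 55 × 0.9 = 49.5 (protocol 50).
- Enrollment A total: about 150, so about 150 more are needed.
- Enrollment B: 150 / 0.9 = 167 (protocol about 170); 170 × 0.9 = 153.

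The 170 reproduces within rounding.

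**2. Composition of the open-label pool.** These are planned entrants; the actual population also needs one dose and one post-Baseline safety assessment.
- Vehicle entrants only: 170 / (55 + 170) = 170/225 = 76% from Enrollment B.
- With 55 active-arm entrants (assumed): 170 / (110 + 170) = 170/280 = 61%.

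**3. What the pooled rate measures.** With extension rate p_E, Enrollment B rate p_B and Enrollment B share w:

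pooled = (1 − w) × p_E + w × p_B, so pooled − p_E = w × (p_B − p_E).

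With w = 0.76, each percentage point of difference between the groups moves the pooled rate 0.76 points from the extension rate and 0.24 points from the Enrollment B rate. With w = 0.61 these are 0.61 and 0.39. The sign follows p_B − p_E, which the documents do not give. Equal rates give no distortion.

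**4. Ascertainment, side by side.**

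| | Extension | Enrollment B |
|---|---|---|
| Otomycosis required | Visible fungal elements | No |
| Pruritus and fullness scored | Day OLE15, with scores from the Randomization Period to compare against | Never |
| AE questioning | Yes | Yes |
| Ear examination at end of treatment | As part of sign scoring | Yes, unscored |

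Section 8.1 sets the comparison as any previous visit, so an OLE15 score can be set against the Day 1, 8, 15 and 22 scores where available. Enrollment B has no scores to compare.

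**5. Precision if the groups are split.** Half-width = 1.96 × √(p(1 − p)/n), at an illustrative p = 27.3% (6/22, the Phase 2 14-day miconazole figure for general and administration-site disorders, Table 1):
- n = 55: ±11.8 points
- n = 170: ±6.7 points
- n = 225: ±5.8 points

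**The case against.** The strongest answer is that the rate in patients is reported elsewhere. The Randomization Period summary covers about 110 miconazole subjects, all with a clinical diagnosis and a fungal-elements score above 0 (section 4.1.1), blinded and set against vehicle. Enrollment B does not enter it. This stands, and it limits the point to the open-label table. It does not cover vehicle subjects crossing to active drug, subjects on a second course, or Enrollment B subjects with otomycosis.

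A reader might infer that the pooled table dilutes the AE rate in otomycosis patients by a calculable amount. The documents do not support that. No Enrollment B rate is given. The 6/22 is one system organ class, not an overall TEAE rate, and its exact 95% interval runs from about 11% to 50%. At 11% in the extension and an assumed 15% in Enrollment B, the pooled rate is (55 × 0.11 + 170 × 0.15)/225 = 14%, above the extension rate, so even the direction is open. Some Enrollment B subjects may have otomycosis. Extension subjects are themselves a selected group: fungal elements remained visible after a randomized course, or they stopped treatment for worsening. Their rate is not that of patients in general.

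The ascertainment gap is also narrower than the schedules suggest. Section 8.1 has every subject asked about problems at each visit and makes worsening symptoms reportable even off the scales. Events attributed to otomycosis are to be recorded as worsening of the study disease, which the preferred-term tables can help to separate. This reduces the difference but does not remove it.

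Finally, the listings are split by portion and period, so separate counts could be rebuilt, and no hypothesis test is involved. Section 10 also defers full detail to a separate statistical analysis plan, which is not in the text reviewed and might split the tables. Both are fair, but a listing is not a planned summary, and sections 10.4.4 and 10.5.2 as written call for the combined one.

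**Conclusion.** The point holds as a limit on what the open-label summaries can show. They combine two groups that differ in disease requirement and in how symptom-related AEs are found, and the larger group, 61% to 76% of the pool, is the one in which otomycosis is not required. The 76% rests on the protocol's planning assumptions; the 61% adds an assumed 55 active-arm entrants. The pooled percentage cannot be read as the rate in the extension or in Enrollment B.

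No figure for distortion is justified: it may be zero, and its sign is unknown. Nor should a reader conclude that the trial lacks an undiluted AE rate in subjects with otomycosis, since the Randomization Period supplies one by arm. Sample size, significance level and efficacy analyses are unaffected. This is an inexpensive improvement to the planned tables.

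**What to change.** In sections 10.4.4 and 10.5.2, present the open-label TEAE and SAE summaries in these columns:

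- Optional Open-label Extension, randomized to vehicle (first miconazole course)
- Optional Open-label Extension, randomized to miconazole (second course)
- Enrollment B with otomycosis at Day B1
- Enrollment B without otomycosis at Day B1
- All open-label subjects, the total already planned

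Otomycosis status at Day B1 needs no new procedure: under sections 3.2 and 4.2.1 the investigator must already judge it to choose the ear. Table 4 has no separate entry for it, so the sponsor should confirm that the eCRF records it. If the separate statistical analysis plan already splits the tables, sections 10.4.4 and 10.5.2 should say so.

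The cost is smaller denominators. The vehicle-origin extension column has about ±12 points at n=55, against ±6 for the retained total, at the illustrative 27% rate. The column for Enrollment B with otomycosis may be very small, because section 3.3 directs subjects eligible for both portions to Enrollment A whenever possible. It should then be read as counts.
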